3.2.4 Rationale for Biomarker Assessments

RO7062931 is a GalNAc-targeted LNA-containing single stranded oligodeoxyribonucleotide, complementary to HBV genome-derived mRNA species. With this, a rapid reduction of viral parameters like HBsAg, HBeAg, but also the corresponding mRNAs, is expected. Structural and functional differences between viral genotypes can influence the severity and response to treatment of hepatitis B virus infection ([Kramvis et al, 2005](#)). Blood samples to monitor decline of viral parameters in correlation with administered dose and to establish the viral genotype will be taken at time-points, as indicated in the Schedule of Assessments tables (see [Appendix 1 to Appendix 14](#)).

Based on nonclinical data (and class effect [[Kynamro Solution for injection 189 mg, CHMP-EMA Assessment Report 2013](#)]) RO7062931 is considered of to be low risk for acute reactions; however, cytokines and complement activation will be measured and sentinel dosing will be implemented.

3.2.5 Rationale for Resistance Monitoring

Blood samples to monitor the potential for resistance emergence will be taken at time-points as indicated in the Schedule of Assessments (see [Appendix 1](#) to [Appendix 14](#) and Section [4.6.1.5.4](#)).

3.3 OUTCOME MEASURES

3.3.1 Safety Outcome Measures

The safety outcome measures for this study are as follows:

- Incidence and severity of adverse events, including adverse events of special interest (see Section [5.3.1](#)).
- Incidence of laboratory abnormalities based on hematology, blood chemistry, coagulation and urinalysis test results (see Section [4.6.1.5](#)).
- ECGs (see Section [4.6.1.4](#)).

- Vital signs, including blood pressure, heart rate and temperature (see Section 4.6.1.3).

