3.1.3 Dose-Escalation Stopping Criteria

3.1.3.1 Part 1

Dose-escalation in Part 1 will not be implemented as planned in healthy volunteers dosed with RO7062931, and dosing for a treatment arm/cohort in Part 2 will be discontinued, if one of the below criteria is fulfilled, unless it is obvious that the occurrence is not considered to be related to RO7062931.

Dose-escalation will be stopped if at a dose level, more than 2 of 8 healthy volunteers receiving RO7062931 in Part 1 or, within a treatment arm/cohort in Part 2, more than 2 of 6 patients experience:

- Severe or clinically significant (as defined by the Investigator) RO7062931-related AEs of the same character, or
- Significant RO7062931-related laboratory abnormality of the same character, or
- Clinically significant RO7062931-related changes in vital signs or ECGs of the same character (e.g., QTcF > 500 msec, or > 60 msec longer than the pre-dose baseline, within the first 48 hours post-dose).
- Within two consecutive dose cohorts, four occurrences of any of the above conditions in HVs receiving active drug.

Other findings (regardless of the incidence rates) that at the joint discretion of the Sponsor and the Investigator indicate that dose-escalation (in Part 1) or dosing (in Part 2) should be halted (see Section 4.7).

3.1.3.2 Part 2

In Part 2, in case a cohort is stopped, alternative regimens within a previously tolerated dose/monthly-exposure range could be further investigated or a regimen repeated in the subsequent cohorts by mutual agreement between the Sponsor and Investigator, in order to increase the amount of data within the tolerated dose/monthly-exposure range. Due to the exploratory nature of this clinical study, its conduct can be discontinued at any time at the discretion of the Sponsor.

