4.6.1.3 Vital Signs

Vital signs will be obtained after the subject has been resting in a supine position for at least 10 minutes.

Blood pressure (BP; systolic and diastolic), pulse rate and body temperature (tympanic) will be recorded at the time-points specified in the SoA tables (see [Appendix 1](#) to [Appendix 14](#)). Blood pressure and pulse rate will be performed in triplicate (can be as short as 20 seconds to 1-minute interval between measurements). The mean of three consecutive replicates will be used as the value for the defined time-point. Vital signs should be measured prior to blood draw. When possible, the same arm should be used for all blood pressure measurements.

Blood pressure and heart rate should be obtained in a quiet room at a comfortable temperature, with the subject's arm unconstrained by clothing or other material. Where possible all measurements will be obtained from the same arm and, with the same cuff size, using a well-calibrated automatic instrument with a digital readout, throughout the study (the "ideal" cuff should have a bladder length that is 80% and a width that is at least 40% of arm circumference [a length-to-width ratio of 2:1]). The study subject should be asked to remove all clothing that covers the location of cuff placement. The individual should be comfortably seated, with the legs uncrossed, and the back and arm supported, such that the middle of the cuff on the upper arm is at the level of the right atrium (the mid-point of the sternum).

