Appendix 9 Schedule of Assessments – Part 2b, PoM (5 Doses QW), Main Table

Period	Screening	Period 1								Discontinua- tion ^e	Follow Up Visit	Follow Up Visit	Follow Up Visit	Follow Up Visit	Follow Up Visit	Follow Up Visit
		Day -1	Day 1	Day 2	Day 8	Day 15	Day 22	Day 29	Day 30							
Day	D-56 to D-2	Day -1	Day 1	Day 2	Day 8	Day 15	Day 22	Day 29	Day 30		Day 36	Day 43	Day 50	Day 57	Day 85	Day 113 ^h
Time Relative (h)	***	***	0	24	168	336	504	672	696	***	840	1008	1176	1344	2016	2688
Visit Window	notime										+/-1	+/-1	+/-1	+/-2	+/-7	+/-7
Assessments																
Informed Consent	X															
Eligibility	X	X														
Demography	X															
Medical History	X															
Fibroscan ^a	X															
Physical Examination ^k	X	X	X		X	X	X	X		X	X	X	X	X	X	X
Vital Signs	X	X	4	X	2	2	2	4	X	X	X	X	X	X	X	X
ECG-12 lead	X	X	4	X	X	X	X	4	X	X	X	X	X	X	X	X
Hematology ^d	X	X		X	X ^b	X ^b	X ^b	X ^b		X	X	X		X	X	X
Blood Chemistry ^d	X	X		X	X ^b	X ^b	X ^b	X ^b		X	X	X		X	X	X
Urinalysis ^d	X	X		X	X ^b	X ^b	X ^b	X ^b		X	X	X		X	X	X
Serology	X															
Coagulation ^d	X	X		X	X ^b	X ^b	X ^b	X ^b		X	X	X		X	X	X
Inflammatory Markers ⁱ			3	X	2	2	2	2	X							
Autoantibodies ^m			X ^b			X ^b		X ^b						X	X	X
ADA ⁱ			X ^b			X ^b		X ^b						X	X	X
Alpha fetoprotein	X															
RBR DNA			X ^b													
Urine Kidney Biomarkers			X ^b	X	X ^b	X ^b	X ^b	X ^b	X	X	X			X	X	X
Blood Liver Biomarker			X		X	X ^b	X ^b	X ^b	X ^b		X	X		X	X	X
Pregnancy Test ^f	X	X								X				X	X	X
FSH ^g	X															
Substance Use	X	X														
Administration of Study Medication			X		X	X	X	X								
PK Blood Sample ^d			7	X	2	2	2	7	X	X	X	X	X	X	X	X
Urine PK Sample			2													

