Appendix 10 Schedule of Assessments – Part 2b, PoM (5 Doses QW), Detailed Table

Period	Day	Scheduled Time (h)	Vital Signs	ECG-12 lead	Inflammatory Markers	Autoantibodies	ADA	Urine Kidney Biomarkers	Blood Liver Biomarker	PK Blood Sample	Urine PK Sample ^b	NUC PK Sample	HBsAg Quantitative	HBsAg, HBeAg Qualitative, HBcAg HBsAg/Anti-HBs Complex Anti HBe/AntiHBs/Anti HBc	HBV DNA, HBV TNA, Viral Resistance Monitoring	
Screening	D-56 to D-2		x	x									x	x	x	
	Day -1		x	x					x				x			
Period 1	Day 1	Predose	x	x	x	x	x	x		x		x		x	x	
		0									x					
		0.5									x					
		1	x	x							x					
		2									x		x ^a			
		3														
		4	x	x							x	x				
		6									x					
		8	x	x	x						x					
	Day 2	24	x	x	x			x	x	x			x			
	Day 8	Predose	x	x	x				x	x	x			x	x	x
		2	x		x						x					
	Day 15	Predose	x	x	x		x	x	x	x	x			x	x	x
		2	x		x						x					
	Day 22	Predose	x	x	x				x	x	x			x	x	x
		2	x		x						x					
	Day 29	Predose	x	x	x		x	x	x	x	x		x	x	x	x
		0.5									x					
		1	x	x							x					
		2									x		x ^a			
4		x	x	x						x						
6										x						
Day 30	8	x	x							x						
	24	x	x	x				x		x						
Discontinuation		x	x					x	x	x		x	x	x		
Follow Up Visit	Day 36		x					x	x	x			x			
	Day 43		x	x						x			x	x	x	
	Day 50		x							x			x			
	Day 57		x	x			x	x	x	x			x	x	x	
	Day 85		x	x			x	x	x	x			x	x	x	
	Day 113		x	x			x	x	x	x			x	x	x	

a) One sample to be taken at any point between 2-4 hours post-dose.

b) Urine collection periods [0-4] and [4-8] hours post-dose.

Appendix 11
Schedule of Assessments – Part 2c, QW Doses for 24 Weeks, Main Table

Period	Screening		Treatment Period									Discontinuation ^e	Follow Up	Follow Up	Follow Up	Follow Up	Follow Up	Follow Up	Follow Up	Follow Up	Follow Up
	D-28 to D-4	Day -7 to -4	Day 1	week 2	week 4	week 8	week 12	week 13	week 18	week 24	week 25		week 26	week 28	week 30	week 32	week 34	week 36	week 40	week 44	week 48
Day	notime			+/-3	+/-3	+/-7	+/-7		+/-7	+/-7		+/-3	+/-3	+/-3	+/-3	+/-3	+/-7	+/-7	+/-7	+/-7	
Assessments																					
Informed Consent	X																				
Eligibility	X	X																			
Demography	X																				
Medical History	X																				
Fibroscan ^a	X																				
Physical Examination ^k	X									X		X								X	
Vital Signs ^l	X		X	X	X	X				X		X								X	
ECG-12 lead	X									X		X								X	
Hematology ^d		X	X ^b	X ^b	X ^b	X ^b	X ^b		X ^b	X ^b		X	X			X				X	
Blood Chemistry ^d		X	X ^b	X ^b	X ^b	X ^b	X ^b		X ^b	X ^b		X	X			X				X	

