Physical Examination ^k	X															X
Vital Signs ⁱ	X		X	X	X	X										X
ECG-12 lead	X															X
Hematology ^d		X		X ^b	X ^b	X ^b	X ^b		X ^b	X ^b		X ^b	X ^b	X ^b	X ^b	
Blood Chemistry ^d		X		X ^b	X ^b	X ^b	X ^b		X ^b	X ^b		X ^b	X ^b	X ^b	X ^b	
Urinalysis ^d		X		X ^b	X ^b	X ^b	X ^b		X ^b	X ^b		X ^b	X ^b	X ^b	X ^b	
TSH	X															
Viral Serology ⁿ	X															
Coagulation ^d		X		X ^b	X ^b	X ^b	X ^b		X ^b	X ^b		X ^b	X ^b	X ^b	X ^b	
Inflammatory Markers ^j			X	X	X	X	X			X						X
Autoantibodies (screening) ^o	X															
Autoantibodies (monitoring) ^m			X ^b			X ^b	X ^b		X ^b	X ^b						X ^b
ADA			X ^b		X ^b	X ^b	X ^b		X ^b	X ^b		X ^b	X ^b	X ^b	X ^b	
Alpha fetoprotein		X														
RBR DNA			X ^b													
Pregnancy Test ^f		X														

Appendix 13
Schedule of Assessments – Part 2c, QW Doses for 48 Weeks, Main Table (cont.)

Period	Discontinuation ^e	Follow Up Visit	Follow Up Visit	Follow Up Visit	Follow Up Visit	Follow Up Visit	Follow Up Visit	Follow Up Visit	Follow Up Visit	Follow Up Visit ^h
Day		week 50	week 52	week 54	week 56	week 58	week 60	week 64	week 68	week 72
		+/-3	+/-3	+/-3	+/-3	+/-3	+/-7	+/-7	+/-7	+/-7
Assessments										
Informed Consent										
Eligibility										
Demography										
Medical History										
Fibroscan ^a										
Physical Examination ^k	X									X
Vital Signs ⁱ	X									X
ECG-12 lead	X									X
Hematology ^d	X		X				X			X
Blood Chemistry ^d	X		X				X			X
Urinalysis ^d	X		X				X			X
TSH										
Viral Serology ⁿ										
Coagulation ^d	X		X				X			X
Inflammatory Markers ^j	X		X							
Autoantibodies (screening) ^o										
Autoantibodies (monitoring) ^m	X									X
ADA	X									X
Alpha fetoprotein										
RBR DNA										
Urine Kidney Biomarkers ^p	X		X							
Pregnancy Test ^f	X									X

Appendix 13
Schedule of Assessments – Part 2c, QW Doses for 48 Weeks, Main Table (cont.)

Period	Screening		Treatment Period													
	D-28 to D-4	Day -7 to -4	Day 1	week 2	week 4	week 8	week 12	week 13	week 18	week 24	week 25	week 30	Week 36	Week 42	week 48	week 49
	notime			+/-3	+/-3	+/-7	+/-7		+/-7	+/-7		+/-7	+/-7	+/-7	+/-7	
Assessments																
FSH ^g	X															
Substance Use		X														
Medications ^c			X													
PK Blood Sample ^q			7	X	2	2	7	X	2	7	X	2	2		7	X
Urine PK Sample ^r			2				2			2			2		2	
NUC PK ^s			2													
HBsAg Quantitative		X	X ^b	X ^b	X ^b	X ^b	X ^b	X ^b	X ^b	X ^b	X ^b	X ^b	X ^b	X ^b	X ^b	X ^b

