HBsAg, HBeAg Qualitative; HBsAg/Anti-HBs Complex; Anti Hbe; AntiHBs		X	X ^b		X ^b	X ^b	X ^b		X ^b	X ^b					X ^b	
Viral Genotypes			X ^b													
HBV DNA, Viral Resistance sequencing		X	X ^b		X ^b	X ^b	X ^b		X ^b	X ^b					X ^b	
HBV RNA, HBcrAg			X ^b		X ^b	X ^b	X ^b		X ^b	X ^b					X ^b	
Clinical Genotyping			X ^l													
Ambulatory Visit	X	X	X	X	X	X	X	X	X	X	X	X	X	X	X	X
Randomisation			X													
Adverse Events	X	X	X	X	X	X	X	X	X	X	X	X	X	X	X	X

Appendix 13
Schedule of Assessments – Part 2c, QW Doses for 48 Weeks, Main Table (cont.)

Period	Discontinuation ^e	Follow Up Visit	Follow Up Visit	Follow Up Visit	Follow Up Visit	Follow Up Visit	Follow Up Visit	Follow Up Visit	Follow Up Visit	Follow Up Visit ^h
Day		week 50	week 52	week 54	week 56	week 58	week 60	week 64	week 68	week 72
		+/-3	+/-3	+/-3	+/-3	+/-3	+/-7	+/-7	+/-7	+/-7
Assessments										
FSH ^g										
Substance Use										
Medications ^c										
PK Blood Sample ^q	X	X	X	X						
Urine PK Sample ^r										
NUC PK ^s										
HBsAg Quantitative	X	X	X	X	X	X	X	X	X	X
HBsAg, HBeAg Qualitative; HBsAg/Anti-HBs Complex; Anti Hbe; AntiHBs	X		X		X	X	X	X	X	X
Viral Genotypes										
HBV DNA, Viral Resistance sequencing	X		X		X	X				X
HBV RNA, HBcrAg	X		X		X	X				X
Clinical Genotyping										
Ambulatory Visit	X	X	X	X	X	X	X	X	X	X
Randomisation										
Adverse Events	X	X	X	X	X	X	X	X	X	X
Previous and Concomitant Treatments	X	X	X	X	X	X	X	X	X	X

Appendix 13

Schedule of Assessments – Part 2c, QW Doses for 48 Weeks, Main Table (cont.)

- a) For those patients who do not have a liver biopsy, Fibroscan® or equivalent test within the past 6 months from Screening.
- b) Pre -dose.
- c) Daily administration of NUC and weekly clinic SC administration of RO7062931 or RO7062931 and PEG-IFN
- d) Blood sample for RO7062931 PK and safety laboratory assessment will also be collected in the event of an SAE.
- e) Discontinuation visit: in case of early termination, a patient should be called for this visit and assessments should be performed as listed.
- f) Blood beta -human chorionic gonadotropin (β -HCG) for pregnancy test at screening, other occasions, at any time a secondary amenorrhea of more than 1 week occurs.
- g) FSH only for females and to confirm post -menopausal status.
- h) If necessary, the patients may be asked to return for additional follow-up visits.
- i) Body weight will be measured at each visit for dosing

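### Part 2c schedules no on-treatment vital signs from Week 8 until Week 24 (Appendix 11) or Week 48/49 (Appendix 13), leaving asymptomatic change unmeasured, mainly in Cohort 10

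*Combined protocol and SAP*

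**What the plan says.** Vital signs are a safety outcome (Section 3.3.1: "Vital signs, including blood pressure, heart rate and temperature") and one of the monitoring methods named in Section 5.2. Section 4.6.1.3 sets no timing of its own: the measurements "will be recorded at the time-points specified in the SoA tables". For Part 2c those tables are Appendix 11 ("Schedule of Assessments – Part 2c, QW Doses for 24 Weeks, Main Table") and Appendix 13 (the 48-week equivalent).

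| On-treatment marks | Appendix 11 | Appendix 13 |
|---|---|---|
| Vital signs | Day 1, Weeks 2, 4, 8, 24 | Day 1, Weeks 2, 4, 8, then only the last treatment column |
| Hematology | Day 1, Weeks 2, 4, 8, 12, 18, 24 | Weeks 2, 4, 8, 12, 18, 24, 30, 36, 42, 48 |

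Both vital-signs rows also mark screening, the discontinuation visit and one late follow-up visit. In the text version of Appendix 13 the last on-treatment mark sits under Week 49. Items meant to be taken before dosing share that column, so Week 48 may be intended.

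The footnote attached to the row adds only this: "Body weight will be measured at each visit for dosing".

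The stopping criteria in Section 3.1.3.1 reach Part 2 as well: "dosing for a treatment arm/cohort in Part 2 will be discontinued, if one of the below criteria is fulfilled". One criterion is "Clinically significant RO7062931-related changes in vital signs or ECGs of the same character", with a threshold in Part 2 of more than 2 of 6 patients.

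**The concern.** A listed safety outcome that also feeds a cohort stopping criterion goes unscheduled for most of the treatment period, while blood sampling for safety continues at regular visits in the same tables.

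The reassurance from earlier parts does not reach this window. Section 1.2.2 reports no vital-sign signal, but in patients that covers at most five weekly doses, up to 3 mg/kg, without PEG-IFN. Section 1.3.2 supports up to 4 mg/kg per week for up to 48 weeks in Part 2c. Section 1.3.1 expects liver steady state at about 13 weeks, which falls inside the gap. Section 1.1 itself regards PEG-IFN as carrying important safety and tolerability risks.

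At stake is asymptomatic change in blood pressure, pulse or temperature during prolonged dosing. Section 5.3.5.5 makes a vital-sign value reportable if the investigator judges it clinically significant, even without symptoms, but that needs a reading. In Cohort 10 the Week 12 and Week 24 interim looks (Section 6.11) would have no scheduled vital signs later than Week 8. Part 2c also has no control group, and Section 3.2.3 compares its safety data qualitatively with Part 2a/2b placebo patients, who were measured throughout.

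**Working it through.** The plan states no figure for this, so the check is a count from the tables.

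**Inputs.** Vital-signs marks as tabulated above. Dosing is once weekly for up to 24 weeks in Cohort 9 and up to 48 weeks in Cohort 10 (Section 4.4.2.1), with Week 1 = Day 1.

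**Is the gap filled elsewhere?** Appendices 12 and 14 list PK samples only. The footnote covers body weight only. The ECG and physical-examination rows of Appendices 11 and 13 are blank between screening and Week 24 or the last treatment column, so heart rate cannot be recovered from ECGs.

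**Gap and doses.** Gap = next marked week − 8. Doses in the gap are the dosing weeks strictly between the two readings, plus one if the Week 8 reading precedes that day's dose.

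| | Gap (weeks) | Doses strictly between | Adding the Week 8 dose | Gap as share of treatment |
|---|---|---|---|---|
| Appendix 11, to Week 24 | 24 − 8 = 16 | Weeks 9–23 = 15 | 16 | 16/24 = 67% |
| Appendix 13, to Week 48 | 48 − 8 = 40 | Weeks 9–47 = 39 | 40 | 40/48 = 83% |
| Appendix 13, to Week 49 | 49 − 8 = 41 | Weeks 9–48 = 40 | 41 | 41/48 = 85% |

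As shares of planned doses, the strict counts are 15/24 = 63% and 39/48 = 81% (40/48 = 83% if the last mark is Week 49).

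**Dosing weeks with a scheduled reading.** Appendix 11: 5/24 = 21%. Appendix 13: 4/48 = 8%, or 5/48 = 10% if the last mark is Week 48.

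**Comparison with Part 2b.** Appendix 9 ("Schedule of Assessments – Part 2b, PoM (5 Doses QW), Main Table") takes 4 + 2 + 2 + 2 + 4 = 14 dosing-day readings over five doses. Appendix 7 takes 4 + 2 + 2 + 4 = 12 over four. Every weekly dose had a reading.

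**With the proposed marks.** Appendix 11: 7/24 = 29%, with gaps after Week 8 of 4, 6 and 6 weeks. Appendix 13: 11/48 = 23%, with gaps of 4, 6, 6, 6, 6, 6 and 6 weeks, plus 1 week if the last existing mark is Week 49.

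**Illustration only.** Suppose a transient change lasts d weeks, starts at a uniformly distributed time in the present gap, and no unscheduled reading is taken. The durations and the uniform onset are assumptions and do not come from the documents. The chance that a scheduled reading meets the change is Σ min(d, gap) / Σ gap.

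| | d = 2 | d = 4 | d = 6 |
|---|---|---|---|
| Appendix 11 now | 2/16 = 12.5% | 4/16 = 25% | 6/16 = 37.5% |
| Appendix 11 proposed | 6/16 = 37.5% | 12/16 = 75% | 16/16 = 100% |
| Appendix 13 now (last mark Week 48) | 2/40 = 5% | 4/40 = 10% | 6/40 = 15% |
| Appendix 13 proposed | 14/40 = 35% | 28/40 = 70% | 40/40 = 100% |

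If the last mark is Week 49, the Appendix 13 figures are 4.9%, 9.8% and 14.6% now, against 15/41 = 37%, 29/41 = 71% and 100%. The 100% entries arise because a 6-week duration equals the longest proposed gap.

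**The case against.** The strongest reply is that this is a deliberate taper that breaks no rule. Timing is left to the schedule, and the schedule sets it. The vital-signs analysis is individual listings with optional tables (Section 6.5.3), so no estimate depends on mid-treatment readings. Four readings over eight weeks precede the gap, including on PEG-IFN, and earlier parts showed nothing. Patients attend weekly, stay until post-dose assessments are done, and are asked about adverse events at each contact (Sections 4.4.2.1 and 5.3.1). Nothing bars unscheduled readings. Cohort 9 enrols first and has a Week 24 reading. Part 2c excludes any history of clinically significant cardiovascular disease. The only itemised PEG-IFN monitoring table is hematological (Section 5.2.1.3), and those tests are scheduled throughout.

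Much of this stands. It confines the concern to asymptomatic change, and a lighter schedule than Part 2b is reasonable. Two further points are also fair. The vital-sign stopping criterion is narrow, and other criteria sit beside it. The assessment order in Section 4.6.1 puts vital signs before dosing, so an added reading would probably be pre-dose and would not catch acute post-dose change. Neither point explains why a named safety outcome should have no scheduled reading for about 40 weeks of first extended dosing with PEG-IFN, when patients are already in clinic for safety bloods.

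**Conclusion.** The concern holds as a proportionate, inexpensive improvement to safety monitoring. It does not threaten any efficacy conclusion. During treatment, scheduled vital signs are absent for 16 weeks (15–16 doses) under Appendix 11 and for 40–41 weeks (39–41 doses) under Appendix 13, unless the patient has a discontinuation visit. Cohort 10 is the main case: it has the longer gap, it adds PEG-IFN, and there the vital-sign stopping criterion would rest on unscheduled readings throughout the gap.

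The conclusion rests on the table marks as read, with the Week 48/49 ambiguity carried through, and on the dose counts. It does not depend on the illustrative detection percentages. Giving Cohort 10 the greater weight is a judgement from treatment length and the protocol's general statement on PEG-IFN risk. The documents name no specific vital-sign risk.

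**What to change.** In the vital-signs rows, add marks at Weeks 12 and 18 in both appendices, and at Weeks 24, 30, 36, 42 and 48 in Appendix 13. Correct the final Appendix 13 mark to the intended week at the same time. This adds two marks to Appendix 11 and up to seven to Appendix 13, and reduces the longest scheduled on-treatment gap to 6 weeks.

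Each added assessment takes about 10 minutes' supine rest plus triplicate blood pressure and pulse and a temperature (Section 4.6.1.3). All fall at clinic visits where safety laboratory samples are already drawn, so no new visit, staff or equipment is needed.

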3.3.2 Pharmacokinetic (PK) and Pharmacodynamic (PD) Outcome Measures

3.3.2.1 Pharmacokinetic Outcome Measures

The PK evaluations for this study are as follows:

Blood and urine samples will be collected to evaluate the RO7062931 and if applicable metabolite(s) PK, as specified in the Schedule of Assessment tables (see [Appendix 1 to Appendix 14](#)). Plasma and urine concentrations will be measured by specific validated methods.

The following plasma and urine PK parameters will be calculated for RO7062931 (and its metabolites, as appropriate), when possible, using non-compartmental methods:

- C_{max} : maximum plasma concentration.
- t_{max} : time to reach the maximum plasma concentration.
- AUC_{0-inf} : area under the plasma concentration-time curve from time zero to infinity.
- AUC_{0-last} : area under the plasma concentration-time curve from time zero until the last quantifiable time-point.
- Additional PK parameters may be calculated from available data including:
 - k (terminal elimination rate constant),
 - $t_{1/2}$ (terminal elimination half-life),
 - CL (total clearance)
 - V_{ss} (volume of distribution).
- Urine PK parameters may be calculated with available data including:
 - A_e - cumulative amount of drug excreted in urine over a 24hour period or over defined time periods linked to the pools of urine collected.
- In Part 2: sparse sampling for tenofovir (including tenofovir alafenamide, if approved for HBV and applicable), entecavir, adefovir and telbivudine will be made to determine patient compliance.

